Hypothesis 2. Veteran-supporting partner dyads participating in SAFER will show improved suicide related coping in comparison to I-SPI. Specifically, we predicted Veterans would experience improvement in suicide-specific coping (Hypothesis 2A) and the supporting partner would demonstrate greater resource knowledge and support of Veteran’s coping efforts (Hypothesis 2B).

Hypothesis 3. Veteran- supporting partner dyads participating in SAFER will show reductions compared to I-SPI on interpersonal appraisals that are related to suicide risk. Specifically, we predicted Veterans would experience reduced perceived burdensomeness and thwarted belongingness (Hypothesis 3A) while supporting partners would experience reduced caregiver burden (Hypothesis 3B).

Methods

Overview

The study is designed as a randomized controlled study comparing SAFER to I-SPI in a sample of thirty-nine Veteran-supporting partner dyads struggling with recent or past suicidal ideation. Outcomes were evaluated using two follow-up assessments (post-treatment and extended follow-up) that were. Due to the difficulty of recruiting this specialized sample, participants were re-contacted for a given assessment until it was finally completed. All

procedures and instruments were approved by an institutional review board. Given the novel nature of the SAFER intervention, the sample intentionally was recruited for having moderate to high, but not extreme immediate risk.

Participants

Eligible Veterans were at moderate risk for suicide, defined as: having endorsed recent passive or active suicidal ideation (within the past 3 months) or a lifetime history of a suicide attempt. Additionally, Veterans must have been receiving care at the VA and have had an available, consenting, and qualifying supporting partner to participate. Supporting partners needed to meet at least three (two for nonrelatives) of five criteria inclusion criteria established by (Pollak & Perlick, 1991): 1) is a spouse, co-habiting significant other or parent; 2) has more frequent contact than any other caregiver; 3) helps to support the patient financially; 4) is contacted by treatment staff for emergencies; 5) has been involved in the patient's treatment.

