The SAFER intervention is a novel, manualized, 90-minute dyad-based intervention that typically includes a joining session, two treatment sessions, and a booster. SAFER follows standard skills training session format and include: 1) brief check-in with brief assessment of mood, current level of suicidality and use of safety plan; 2) homework review; 3) teaching of new material and skill; 4) in-class practice of the skill; and assignment of homework/outside practice of skill /development of safety plan. Session content includes the use of psychoeducation,

communication skills training and revision and development of both the Veteran and a complementary supporting partner SPI. The SAFER treatment goal is to provide the tools and structure to support social support involvement in Safety Planning Intervention for Veterans at moderate risk for suicide (**Table 1**).

Treatment Fidelity. A fidelity scale was developed during the prior open trial plot testing to assess core features of SAFER's structure, contents and treatment principles, along with general clinical competence (e.g., building rapport, crisis management, etc.). This 14-17 item scale (13 general competence items and 1-4 session-specific items) was rated on a 4-point Likert scale (where 0 = unacceptable and 3 = excellent). were made by one trained rater. The rater was trained by the Principal Investigator and research staff. It was a one-day training to review components of the treatment manual, instruction in group therapy principles and group didactics, and suicide risk assessment. Additionally, the rater read the 51-page manual inclusive of session handouts and worksheets. All intervention sessions were recorded, and a randomization scheme was generated to have seven sessions randomly selected for review. Clinicians are required to maintain a total score of 80% or above on each session to demonstrate acceptable adherence to the intervention. Clinicians whose ratings fall below this criterion were given additional supervision and their adherence was monitored until satisfactory adherence was regained. The average percentages on the adherence scale ranged from 82 to 100 with the mean score being 90.7. No interventionists ever dropped below the 80% adherent threshold and therefore no re-training was required throughout the trial.

Measures

Primary Outcome Measure (Hypothesis 1)

Veteran suicidal ideation. Moderate suicidality was measured to determine eligibility

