The Level 2 equation models respondents' trajectories based on condition (SAFER=1; I-SPI=0). Due to limited power, we were sparing with our controls and limited them to those considered most relevant to Veteran risk (history of attempt; 0= No attempts; 1=Has 1+ attempts), ability to collaborate with the supporting partner (nature of relationship between partners; 1=Romantic; 0=All others), and attrition (age). The treatment effect of SAFER is modeled as the effect of condition on change in functioning over time (β_{11}) after controlling for differences between conditions at baseline (β_{01}) and demographic controls (all other β s).

As Veterans and supporting partners were assessed on separate outcomes that in many cases were assessed weeks to months apart from one another, we estimated separate trajectories for each outcome without needing to account for dyadic dependence.

Results

Descriptives

Participant characteristics at baseline can be found on Table 3. Consistent with the Veteran population in the recruitment region, the sample was generally middle-aged, more likely to be black, somewhat more likely to be Hispanic/Latino and somewhat more likely to be unemployed than the general population. The final sample of 39 Veteran-supporting partner dyads included a range of supports including 14 romantic partners, 13 family members of Veterans, and 12 close friends. Although supporting partners were not required to be Veterans, a third of supporting partner (n=13) identified as Veterans themselves. 19 Veterans reported a history of one or more suicide attempts. As can be seen on Table 3, participants were generally similar across both conditions with respect to demographics characteristics as well as all outcomes. This highlights the effectiveness of random assignment in our small sample and suggests the groups are roughly comparable for treatment analyses.

Impact of Treatment Condition on Change in Outcomes over Time

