The full model examining change in C-SSRS rated severity of suicidal ideation can be found in **Table 4**. As can be seen in the top half of **Table 4**, Veteran suicidal ideation did not significantly differ at baseline by condition or demographic controls. However, there was a significant effect of treatment condition on their trajectories over the course of the study. Specifically, Veterans in the active SAFER condition were predicted to see sharper declines in suicide ideation than those in the control group ($B = -0.37$; $p = .032$). In order to clarify the impact of treatment on trajectory over time, we then calculated the slope-intercept trajectory within each condition. Veterans in the SAFER condition experienced significant declines in severity of suicidal ideation while there was little change over time in the control condition.

This pattern of findings was replicated when examining the impact of treatment participation on coping strategies (Hypothesis 2). Specifically, a significant treatment-by-time

interaction emerged when predicting Veteran suicide-related coping ($B=1.40$; $p=.028$).

Examination of simple slopes highlights that Veterans in SAFER reported marginal increases in suicide-related coping (Simple Slope= 0.88 ; $p=.080$) while Veterans in I-SPI reported non-significant declines in coping. Similarly, a treatment effect emerged for supporting partners support of Veteran coping ($B=0.79$; $p=.034$). Specifically, while supporting partners in I-SPI provided marginally less support over time, caregivers in SAFER maintained their efforts to support Veteran coping.

Contrary to expectations, self-reported appraisals of relational factors and self-efficacy were not impacted by condition for either Veterans or supporting partners. In fact, modeling trajectories across both conditions highlight that most appraisal variables are expected to be stable across the length of the study.

Impact of Controls

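### The two positive Hypothesis 2 results (p=.028, .034) come from five non-primary tests with no stated error control; they fail Holm, the false-discovery answer depends on the family, and the text presents them too firmly

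*Combined protocol and SAP*

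**What the plan says.** In the combined protocol and SAP, the Measures section gives the heading "Primary Outcome Measure (Hypothesis 1") to C-SSRS ideation and to nothing else. Study Hypotheses adds five further outcomes:

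- Hypothesis 2A, Veteran coping: "we predicted Veterans would experience improvement in suicide-specific coping (Hypothesis 2A").
- Hypothesis 2B, the supporting partner's knowledge and support of coping.
- Hypothesis 3A, two INQ-15 subscales: "we predicted Veterans would experience reduced perceived burdensomeness and thwarted belongingness (Hypothesis 3A").
- Hypothesis 3B, caregiver burden: "supporting partners would experience reduced caregiver burden (Hypothesis 3B").

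The Analytic Strategy fits one model per outcome ("we estimated separate trajectories for each outcome without needing to account for dyadic dependence") and takes one coefficient from each as the effect: "The treatment effect of SAFER is modeled as the effect of condition on change in functioning over time". It states no alpha, family, testing order or multiplicity adjustment.

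Under Results, Impact of Treatment Condition on Change in Outcomes over Time, Veteran coping shows "a significant treatment-by-time" interaction (B=1.40, p=.028). For partners, "a treatment effect emerged for supporting partners support of Veteran coping" (B=0.79, p=.034). These results are introduced as a replication of the Hypothesis 1 pattern. The Hypothesis 3 outcomes are reported as unaffected by condition, without p-values.

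**The concern.** Several outcomes are each read against an unadjusted threshold, and those that fall below it are described as treatment effects. The more tests there are, the likelier it is that at least one falls below by chance. Here the two positive p-values lie just under .05, so the status of Hypothesis 2 turns on an error-control rule that the plan never states. The replication wording adds to this: it invites the reader to treat the coping results as independent support for the primary finding, at the same level of confidence.

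What is at stake is what the trial may conclude about coping. The Hypothesis 1 test, taken as the single primary test, is untouched.

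**Working it through.** **Inputs.** From the Results: p=.028 (2A), p=.034 (2B), p=.032 (Hypothesis 1). From Study Hypotheses and Analytic Strategy: five outcomes under Hypotheses 2 and 3, one test each. Two inputs are assumed. The level is .05, inferred because .034 is read as an effect and .080 as marginal. Each unreported Hypothesis 3 p-value lies between .05 and 1. The documents contain no adjusted figure to reproduce.

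**Chance of false positives, five independent tests at .05, all nulls true**

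- At least one: 1 − .95^5 = .226.
- Exactly one: 5 × .05 × .95^4 = .204.
- Two or more: .226 − .204, which is .023 before rounding of the parts.

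Positive correlation between outcomes would lower the first figure.

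**Holm over the five tests.** The smallest p gives .028 × 5 = .140. The next gives .034 × 4 = .136, raised to .140. Neither is rejected.

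**Benjamini-Hochberg (BH) over the five tests.** The adjusted value is the smallest of 5p(k)/k from that rank upward. Rank 1 gives .028 × 5 = .140 and rank 2 gives .034 × 5/2 = .085, so both are .085 when the other three p-values are large. If all three exceed .05, rank 3 gives more than .083, rank 4 more than .0625 and rank 5 more than .05. The adjusted value therefore stays above .05 whatever the Hypothesis 3 p-values are.

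**Other families** (BH values for the six-test family assume large Hypothesis 3 p-values)

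| Family | Holm | BH |
|---|---|---|
| Hypotheses 2 and 3 (five tests) | .140 each | .085 each |
| Hypothesis 2 only (two tests) | .028 × 2 = .056 each | .034 × 2/2 = .034 each |
| Hypotheses 1 and 2 (three tests) | .028 × 3 = .084 each | .034 × 3/3 = .034 each |
| All six tests | .028 × 6 = .168 each | .034 × 6/3 = .068 each |

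**Joint reading.** If Hypothesis 2 requires both 2A and 2B, its p-value is the larger of the two, .034, with no adjustment inside it. Holm across Hypotheses 2 and 3 then gives .034 × 2 = .068.

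**Rounding.** At the lowest values consistent with the printed figures (.0275 and .0335), Holm over five is .1375, BH over five is .084, and Holm within Hypothesis 2 is .055. No conclusion changes.

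**Does the Hypothesis 2 pattern match Hypothesis 1?** For ideation, the Results describe a significant decline under SAFER and little change in controls. For Veteran coping, the SAFER slope is only marginal (0.88, p=.080) and the control decline is non-significant. For partners, SAFER held support steady while controls fell marginally, whereas Hypothesis 2B predicted greater knowledge and support. Neither coping outcome shows a significant improvement within SAFER.

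**The case against.** The other side has real points.

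- **The family is a choice.** The documents set out coping and interpersonal appraisals as separate hypotheses with separate measure headings. Within Hypothesis 2, BH gives .034 and passes, and so does Hochberg. Over five tests, BH would also pass at a 10% rate. All of this stands. A reader might infer that the two results fail every form of multiplicity control; the documents do not support that.
- **Two positives out of five is uncommon by chance.** The 2.3% figure stands, subject to independence. A reader might infer that the coping findings are false positives; nothing here shows that.
- **A fixed sequence in the order of the hypotheses would have passed Hypothesis 2.** True, but none is stated. Numbering hypotheses is not a testing procedure, and a rule picked after the p-values are known does not control error.
- **The text is partly candid.** Only 2A is literally called significant, and nowhere is Hypothesis 2 said to be confirmed. The document describes a small trial of initial efficacy, admits limited power, gives exact p-values for the positive tests and discloses the Hypothesis 3 nulls. This limits the harm. It does not supply a label of nominal or exploratory, and it does not justify the replication wording.
- **Small early trials often leave non-primary outcomes unadjusted.** That is acceptable if the p-values are labelled as such, and here they are not.

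**Conclusion.** The point holds as one of unstated error control and over-firm wording. Both Hypothesis 2 results fail Holm in every family tried, from .14 over the five tests down to a narrow .056 within Hypothesis 2. Under BH at 5% they fail when Hypotheses 2 and 3 are pooled and pass within Hypothesis 2 alone. Whether Hypothesis 2 is established thus depends on a rule the plan does not give, and the within-arm slopes do not bear out a replication of the primary pattern.

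This rests on an inferred .05 level, on Hypothesis 3 p-values above .05, and on treating outcomes not headed primary as secondary, a word the documents do not use. The section on Impact of Controls does speak of primary hypotheses in the plural. A reader might infer from this that the ideation result belongs in the same family and falls with it (Holm .168 over six). The Measures section heads only C-SSRS ideation as primary, so that reading is not adopted; adding the sixth test would not rescue Hypothesis 2 in any case.

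The fair description of Hypothesis 2 is suggestive. This is a worthwhile, inexpensive correction; it does not invalidate the trial.

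**What to change.** 1. State the significance level and keep C-SSRS ideation as the single confirmatory test.
2. State that the p-values for Hypotheses 2 and 3 are nominal.
3. Tabulate all five condition-by-time estimates, including the three for Hypothesis 3, with 95% CIs, nominal p-values and Holm-adjusted p-values. Name the family used and say that it was chosen after the results were known.
4. Describe the Hypothesis 2 results as suggestive and remove the statement that they replicate the primary pattern.

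The cost is a few table columns and some rewording. The models are already fitted, no new data are needed and the primary test does not change. The one downside is a slightly less favourable statement of Hypothesis 2.

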After screening and consent, Veterans and supporting partners completed separate in-person baseline assessments which included demographic data, Veteran and supporting partner assessments to assess inclusion/exclusion, and measures including the final study outcomes. Each Veteran-supporting partner dyad was then randomly assigned to participate in either I-SPI or SAFER with a one to one ratio using a block randomization scheme. Regardless of randomization, Veterans were allowed to continue with all other VA care, as needed. Outcomes were re-assessed immediately post-intervention and then again through a follow-up assessment at least 3-months post-intervention. To minimize attrition in this difficult to obtain and track sample, participants were initially contacted at the end of their intervention and then re-contacted until one or both provided the post-treatment assessment (Range=0.30-7.47 months from baseline; $M=2.84$ months) and then the follow-up was timed three months from that point or up

until one year from enrollment (Range=3.10-11.43 months from participants' baseline; $M=6.32$ months).

Attrition. Of the 78 participants in the study, 57 gave at least one wave of follow-up (30 Veterans; 27 Supporting Partners). Examination of demographic predictors of attrition found that participants who provided follow-up did not significantly differ from participants who did not with respect to assigned condition, years of education, gender, ethnicity, race, employment status, nature of caregiving relationship, Veteran status of the non-Veteran partner, or any of the baseline levels of the outcome measures. However, age did significantly predict attrition ($t(76) = -2.36; p < .02$), with those providing follow-up being generally older ($M=51.37$ years) than those who did not ($M=42.76$ years).

Individual Suicide-Safety Planning (Control)

As noted above, all participants were able to continue in standard VHA care based on their own determined needs (psychiatry; psychotherapy; and case management by the suicide prevention coordinator). Veterans in the control group were able to update and review their safety plan with a study clinician. Veterans created a full SPI with a study clinician if they did not already have one.

SAFER Intervention (Treatment)

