Although not part of our primary hypotheses, we examined significant effects of controls on the outcomes of interest. Notably, romantic partners of Veterans reported substantially higher overall levels of caregiver burden at baseline ($B=17.66$; $p=.01$) that remained relatively stable over the study. Veterans with romantic partners showed corresponding increases in suicide ideation severity ($B=0.49$; $p=.02$; Table 2) and decreases in suicide-related coping ($B=-1.52$; $p=.04$). In contrast, Veteran history of suicide attempt was associated with only somewhat elevated caregiver burden on baseline ($B=7.22$; $p=.28$) that were offset greater declines in caregiver burden over the study ($B=-2.38$; $p=.03$). Taken together, this indicates that caregivers of Veterans with a history of attempt showed general adaptation as the crisis subsided while romantic partners of Veterans experienced stable high levels of burden that were then followed by worsening functioning for the Veteran over time.

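### An apparently non-significant result on the Hypothesis 3 outcomes, including caregiver burden, is worded as no impact of condition, which the implied precision for burden cannot support

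*Combined protocol and SAP*

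**What the plan says.** Study Hypotheses places caregiver burden among the interpersonal appraisals and predicts, relative to I-SPI, that "supporting partners would experience reduced caregiver burden (Hypothesis 3B"). The Measures section describes the Caregiver Burden Inventory under the same Hypothesis 3 heading.

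Analytic Strategy defines the parameter of interest: "The treatment effect of SAFER is modeled as the effect of condition on change in functioning over time". This is beta_11, a difference in monthly slope. The same section justifies the short covariate list by limited power.

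Under Impact of Treatment Condition on Change in Outcomes over Time, the three outcomes with significant results each get a coefficient and a p-value. For Hypothesis 3 the text says only that "self-reported appraisals of relational factors and self-efficacy were not impacted by condition for either Veterans or supporting partners", and adds that most appraisal variables are expected to be stable when both conditions are modelled together. The sentence does not name caregiver burden, but the Hypothesis 3 grouping puts burden within it.

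Impact of Controls gives coefficients from the burden model for covariates only. Attempt history is linked to "greater declines in caregiver burden over the study ($B=-2.38$; $p=.03"), which is read as adaptation by caregivers as the crisis subsided. At baseline, "romantic partners of Veterans reported substantially higher overall levels of caregiver burden at baseline ($B=17.66$; $p=.01"), while attempt history carries a difference of 7.22 points (p=.28), described as a mild elevation.

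**The concern.** A test that does not reach significance shows that a difference was not detected. It does not show that there is none, unless the interval is narrow enough to exclude differences that matter. Here no interval appears in the text, no equivalence margin or important difference is defined, and only 27 of 39 supporting partners gave any follow-up.

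Caregiver burden deserves particular care. SAFER gives partners an active role in safety planning, and lessening their sense of burden is one of its stated aims. Among the measures described, burden is the one that could most directly register a cost to them. If the statement of no impact is taken at face value, readers may treat the question of partner burden as settled in both directions when the data leave it open.

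**Working it through.** The available text gives no estimate, standard error or interval for condition on burden, so there is no figure to reproduce. The width of the interval can be approximated from another coefficient in the same model.

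**Inputs**
- Attempt-history slope on burden: -2.38 points per month, p=.03 (Impact of Controls).
- Attempt history: "19 Veterans reported a history of one or more suicide attempts", out of 39 (Descriptives).
- Allocation: "with a one to one ratio using a block randomization scheme" (Assessments).
- Mean time from baseline: 2.84 months at post-treatment, 6.32 months at extended follow-up (Assessments).
- Assumed: two-sided 5% level, since none is stated.

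**Step 1: standard error of the attempt-history slope.** SE = |B| / quantile at 1 - p/2.
- Normal: 2.38 / 2.17 = 1.10 points per month.
- t with 34 df: 2.38 / 2.27 = 1.05.

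**Step 2: carry it over to condition.** Both are binary Level 2 predictors of the same slope in the same model, with near-equal splits (19/20 and 1:1). This is an assumption. Three checks bear on it:
- In the burden intercept, the implied SEs are 6.86 for romantic relationship (17.66, p=.01) and 6.68 for attempt history (7.22, p=.28). The ratio is 1.03, against 1.04 expected from the 14/39 and 19/39 splits.
- A design simulation used 39 partners, 27 followed up at random, visit times drawn to match the stated means and ranges, and an assumed within-person correlation of 0.5 to 0.85. The ratio of condition to attempt-history slope SE had median 1.00 and 95% range 0.85 to 1.17.
- The Veteran models report slopes for both condition and romantic relationship. Ideation implies SEs of 0.17 (0.37, p=.032) and 0.21 (0.49, p=.02), ratio 0.82. Coping implies 0.64 (1.40, p=.028) and 0.74 (1.52, p=.04), ratio 0.86. Applying 0.82 to 1.10 gives an SE of 0.90, a half-width of 1.76 per month, and 11.1 points at 6.32 months.

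**Step 3: half-width of the 95% interval.**
- Per month: 1.96 × 1.10 = 2.15 (t version: 2.03 × 1.05 = 2.14).
- At 6.32 months: 2.15 × 6.32 = 13.6 points.
- At 2.84 months: 2.15 × 2.84 = 6.1 points.
- Allowing for rounding of p, degrees of freedom and design imbalance, the SE runs from about 0.87 to 1.32. The half-width is then about 1.7 to 2.6 per month, or 10.7 to 16.4 points at 6.32 months.

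**Step 4: what this means for different estimates.** Under the central SE, any condition slope between about -2.15 and +2.15 per month would be non-significant.
- Estimate near zero: at 6.32 months the interval is about -13.6 to +13.6. It includes a rise or fall of 7.22 and excludes 17.66. At 2.84 months, ±6.1 excludes 7.22 as well.
- A rise of 7.22 at 6.32 months is excluded only if the estimate is below 7.22/6.32 - 2.15 = 1.14 - 2.15 = -1.01 per month.
- The upper limit reaches 17.66 only if the estimate is at least 17.66/6.32 - 2.15 = 2.79 - 2.15 = +0.64 per month.
- For a zero-centred interval to exclude 7.22 at 6.32 months, the SE would have to be 7.22 / (1.96 × 6.32) = 0.58, about half the attempt-history SE.

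**The case against.** The strongest reply is that the borrowed standard error gives a width and not a location. The text reports neither beta_11 nor its p-value for burden. A reader might infer that a substantial rise in partner burden under SAFER cannot be excluded, but the document's figures do not show that. The only burden difference it calls substantial is 17.66 points, and a zero-centred interval excludes that even at the widest half-width of 16.4. If the estimate favours SAFER by more than about 1 point per month, a rise of 7.22 is excluded too. This part of the objection stands.

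Other parts also stand. At the mean post-treatment time the half-width is only about 6 points, and the text does not say how many partners reached the later assessment. The 19/20 and 1:1 splits describe all 39 dyads; the splits among the 27 partners followed up are not given. The values 7.22 and 17.66 are baseline gaps between people, not thresholds for important change, and 7.22 is itself non-significant. The tables are not reproduced in the available text and may hold the estimate.

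A reader might also infer that the document declares SAFER harmless to relatives or Hypothesis 3B firmly refuted. It says neither. It reports a result contrary to expectation, in a trial described as small and aimed at initial efficacy.

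None of this rescues the wording. A statement of no impact is still stronger than a non-significant result can carry in a study that concedes limited power.

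**Conclusion.** The point holds as a matter of wording and reporting. An apparently non-significant condition-by-time result is stated as absence of effect. For burden, the implied 95% half-width of about 2.15 points per month is nearly as large as the 2.38 per month that the same document interprets as a real difference between groups of caregivers. A condition effect of almost that size, in either direction, could sit behind the same sentence.

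The size rests on the condition slope having about the same SE as the attempt-history slope, and on a two-sided 5% level. The first is plausible on three checks but unverified. Whether the interval leaves room for a meaningful rise or fall in burden depends on the unreported estimate. Near zero it does at 6.32 months, judged against 7.22 points; for an estimate sufficiently in SAFER's favour, a rise of that size is excluded. The calculation covers burden only, because the text gives nothing from which to derive precision for the two INQ subscales.

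**What to change.** In the Results sentence on Hypothesis 3, replace the claim of no impact with *no difference was detected*. Report beta_11 with its 95% CI for caregiver burden and for the two INQ subscales, or point to the table if the figures are already there. For burden, give the interval per month and also at 2.84 and 6.32 months, so that both assessment times can be judged. Only if the burden interval allows it, add that a meaningful increase or decrease in partner burden has not been ruled out.

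The fitted models already contain these estimates, so no new data or analysis is needed. The cost is a few lines of text and a slightly less definite conclusion.

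### Impact of Controls words slope differences against the reference group as change within the romantic-partner and attempt-history groups, and the quoted p-values do not test that change

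*Combined protocol and SAP*

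**What the plan says.** Analytic Strategy defines each person's slope as linear change per month. Condition, attempt history, relationship and age enter the slope equation additively. Relationship is coded 1 for romantic and 0 for every other kind. Attempt history is coded 1 for any attempt and 0 for none. Each outcome has its own model.

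Impact of Controls then reports:

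- Ideation: "Veterans with romantic partners showed corresponding increases in suicide ideation severity", B=0.49, p=.02.
- Coping: a decrease for the same Veterans, B=-1.52, p=.04.
- Caregiver burden where the Veteran had a past attempt: "greater declines in caregiver burden over the study", B=-2.38, p=.03.

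The closing sentence says, without a hedge, that "caregivers of Veterans with a history of attempt showed general adaptation as the crisis subsided" and that "romantic partners of Veterans experienced stable high levels of burden that were then followed by worsening functioning for the Veteran over time".

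For treatment condition, the preceding results section goes a step further. After the interaction test on ideation, it says "we then calculated the slope-intercept trajectory within each condition". For coping it gives a SAFER slope of 0.88 (p=.080), "while Veterans in I-SPI reported non-significant declines in coping".

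**The concern.** With 0/1 coding and no interactions between controls, a control's coefficient in the slope equation is the difference in monthly change between the group coded 1 and the group coded 0. B=0.49 would be the same whether ideation in the romantic group rose, stayed flat, or fell more slowly than in the other dyads. Which of these happened depends on the reference group's slope, and the prose does not give it.

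A reader will take p=.02 and p=.04 as evidence that Veterans with romantic partners became more suicidal and coped less well. That is a consequential message from 14 of 39 dyads, and the quoted tests do not address it. The closing sentence carries the same reading over to caregivers of Veterans with a past attempt. Its sequence of partner burden followed by Veteran decline can also be read as a link within dyads.

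**Working it through.** **1. Which coefficients are slope terms.** B=0.49 cannot be a baseline term, because the results say "Veteran suicidal ideation did not significantly differ at baseline by condition or demographic controls". B=-2.38 is worded as change over the study. B=-1.52 is a slope term by inference from its wording as a decrease; if it were a baseline term, that wording would be wrong outright.

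**2. The document's own example.** B and p cannot be re-derived without standard errors or data, but the coping slopes by arm can be checked for consistency. Use SE = |B| / z(1 - p/2), normal approximation.

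- Contrast: 1.40 / 2.197 = 0.637. SAFER slope: 0.88 / 1.751 = 0.503.
- I-SPI slope: 0.88 - 1.40 = -0.52.
- I-SPI SE, arms independent: sqrt(0.637² - 0.503²) = 0.39, so p is about .18. With the SAFER SE instead, p is about .30.

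This agrees with the text. A contrast with p=.028 sits beside two arm slopes that are each non-significant, so a significant difference does not establish change in either group.

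**3. Break-even values (additive model only).**

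- Romantic ideation rises only if the non-romantic slope is above -0.49 per month.
- Romantic coping falls only if the non-romantic slope is below +1.52.
- Attempt-history burden falls only if the no-attempt slope is below +2.38.

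**4. Illustration.** Assumptions: equal arms, equal residual variance, uncorrelated covariates, and baseline shares (14/39 romantic, 19/39 with a past attempt). The documents do not say at which covariate values the arm slopes were calculated, so two readings are shown: at average covariates, and at the non-romantic reference.

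SE of the romantic slope, derived in two ways:

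- Contrast SE × sqrt(25/39): ideation (0.49/2.326) × 0.801 = 0.169; coping (1.52/2.054) × 0.801 = 0.593.
- Condition SE × sqrt(39/14)/2: ideation (0.37/2.144) × 0.835 = 0.144; coping 0.637 × 0.835 = 0.532.

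*Coping.* The mean of the two arm slopes is (0.88 - 0.52)/2 = 0.18.

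- Average reading: 0.18 - 1.52 × 25/39 = -0.79, p about .14 to .18.
- Reference reading: 0.18 - 1.52 = -1.34, p about .01 to .02.

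*Ideation.* No I-SPI slope is given; the text says only that the control arm barely changed. Call it s. The mean of the arms is s - 0.37/2 = s - 0.185.

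| s (assumed) | Average reading: s - 0.185 + 0.49 × 25/39 | Reference reading: s - 0.185 + 0.49 |
|---|---|---|
| -0.1 | +0.03 (p about .84 to .86) | +0.21 (p about .16 to .22) |
| 0 | +0.13 (p about .37 to .44) | +0.31 (p about .03 to .07) |
| +0.1 | +0.23 (p about .11 to .17) | +0.41 (p about .005 to .02) |

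The sign turns negative only if s is below -0.13 (average reading) or -0.31 (reference reading). At s = 0 on the average reading, the romantic slope is +0.31 in I-SPI and -0.06 in SAFER.

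*Burden.* The attempt-history slope is the overall slope minus 2.38 × 20/39 = 1.22, with SE (2.38/2.170) × sqrt(20/39) = 0.785. The text says only that "most appraisal variables are expected to be stable across the length of the study" and gives no figure for burden. For assumed overall slopes of -1, 0 and +1, the attempt-history slope is -2.22 (p about .005), -1.22 (p about .12) and -0.22 (p about .78).

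**5. The sequence claim.** Partner burden and the Veteran outcomes were fitted in separate models, so no model relates one to the other within a dyad.

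**The case against.** The strongest reply is that the directions in the text are probably right. For coping, the reported arm slopes imply a non-romantic slope of about 0.18 + 1.52 × 14/39 = +0.73 (average reading) or +0.18 (reference reading). Both are well below the +1.52 break-even, so the romantic slope is negative either way. For ideation, the illustrated slopes are all positive, and a negative sign needs a control-arm decline that fits poorly with a control arm described as barely changing. This stands for the direction of coping. It does not settle significance, and for ideation it rests on an assumed control slope.

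The second reply is that Tables 2 and 4, cited for ideation, were not visible in the text reviewed. The full model table may give the reference slope, from which a reader could work out the romantic slope. This also stands: the gap is shown for the prose only.

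Three stronger readings are tempting, and the documents do not support them:

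- *That the groups did not change as described.* Nothing in the text shows this. On the reference reading, the coping statement would be largely borne out.
- *That all three p-values are attached to within-group claims.* The phrase beside p=.03 is properly comparative. For attempt history, only the closing sentence goes too far.
- *That the trial's main findings are in doubt.* The section places itself outside the primary hypotheses, and the condition effects do not depend on how the control coefficients are worded.

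**Conclusion.** The point holds as a minor correction to a secondary conclusion. The coefficients 0.49 and -1.52 are slope differences against non-romantic dyads, and p=.02 and p=.04 do not test the increase and decrease stated beside them. The closing sentence then asserts worsening in one group and adaptation in another, with no within-group estimate in the prose for either.

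The within-group statements are untested. The romantic coping slope is likely negative (about -0.79 or -1.34 per month), with p anywhere from about .01 to .18. The romantic ideation slope is undetermined: +0.03 to +0.41 per month across the illustrated cases, with p from about .005 to .86. The attempt-history burden slope is undetermined without the overall slope.

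That the coefficients are slope differences follows from the model and coding alone, with the one inference noted for coping. The numerical ranges rest on the normal approximation, rounded p-values and the assumptions listed in step 4. Only 30 Veterans and 27 partners gave any follow-up. The shares among them are not reported, although the Attrition paragraph says follow-up did not differ significantly by caregiving relationship.

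**What to change.** Either of two changes would do:

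- Restate the two romantic-partner results and the closing sentence as differences in monthly slope relative to the reference group (other relationships; no past attempt).
- Report simple slopes with confidence intervals from the existing fits, at stated covariate values: by relationship for ideation and coping, and by attempt history for burden. Keep the words increase, decrease, worsening and adaptation only where those slopes support them.

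In either case, reword the phrase that places Veteran decline after partner burden so that it does not suggest a modelled link between the two. The comparative wording beside B=-2.38 can stay.

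The cost is a few linear combinations of coefficients already estimated and the rewording of one paragraph, with no new data. The downside is that the paragraph's conclusion may become inconclusive.
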